## VISIT 16: Week 26 post randomization (**study end,** 4 hours)

The following data will be collected at the endpoint:

- i. Auxological
  - a. Height, weight, BMI.
- ii. Glycaemic:
  - a. CGM uploaded for those standard therapy (MDI and CSII)
  - b. 670G uploaded for HCL participants
- iii. Diabetes clinical
  - a. HbA1c
  - b. Blood pressure (average of 2 readings)
  - c. Previous 7 days' total daily dose insulin (basal and bolus proportions for participants on insulin pump therapy)
  - d. Carbohydrate ratios and insulin sensitivity
  - e. Symptomatic hypoglycaemia requiring carbohydrate rescue in the previous 21 days from participant logbook.
- iv. Psychological assessments:
  - a. **Fear of hypoglycaemia**: Hypoglycaemic Fear Survey-II Worry scale: 17-<25years. Children's Hypoglycaemia Fear survey 12 – 17 years.
  - b. **Hypoglycaemia Awareness**: *Hypoglycaemia Awareness Scale (Gold Score) (all ages)*
  - c. **Anxiety**: State-Trait Anxiety Inventory (Child version for 12-15yrs, adult version ≥16-<25yrs).
  - d. **Impact and Satisfaction**: The Diabetes Treatment Satisfaction Questionnaire status and change version (16 <25 years)
  - e. Quality of Life: 12-<25 years: EO-5D-Y,
  - f. **Diabetes specific quality of life**:  $PedsQL Child \ version \ (12 \ years) \ Adolescent \ version \ (13 18 \ years) \ and \ young \ adult \ version \ (18 <25 \ years).$

Page 32 of 85

- g. **Diabetes distress:** Problem Areas in Diabetes (Teen version for 12 17 years, standard version  $\geq 17$ -<25yrs,
- h. Participant reported outcome for Automated Delivery system: INSPIRE Questionnaires: baseline and post-assessment versions Child version (12 year olds), Adolescent version (13-18) and adult version(18-25)
- **Semi structure interview** (all ages)

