End of study assessments	Visit 16:							
	i) Auxological							
	a. Height							
	b. Weight							
	ii) CGM glycaemic data and all secondary glycaemic							
	measures							

	
 
iii) Seated blood pressure (average of 2 readings)
 
iv) Total daily dose, basal and bolus proportion, carbohydrate ratio and insulin sensitivity factor
 
v) Psychological assessments (age specific)
 
vi) Biomarkers
 
vii) Semi structured interview
 
						
Continuous Assessments	Technology interactions/human factors (repeated sampling)						
	through mobile phone app.  ii. Investigator time spent training (carbohydrate counting, HCL training) and support.  iii. Time off work and school  iv. Consumable use (sensors, pump sites)  v. Health care providers expectations and experiences (repeated sampling through mobile phone app)						
Procedures for safety	Safety measures will be recorded including ketone levels.						
monitoring during trial	Establishment of a data safety and monitoring board (DSMB) to scrutinise conduct of the study and study team and to monitor safety data arising from the study in order to determine if stopping the trial is required. Refer appendix 15.12						
Criteria for withdrawal of participants on safety grounds	A subject may terminate participation in the study at any time without necessarily giving a reason and without any personal disadvantage. An investigator can stop the participation of a subject after consideration of the benefit/risk ratio. Possible reasons are:  1. Serious Adverse Events 2. Inability to meet study requirements (e.g. regularly upload pump history to computer) 3. Technical grounds 4. Early termination of the study at the request of the steering committee or data safety monitoring board						

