#### 2. Clinical measures

The compare the difference between HCL insulin delivery vs standard therapy for the following measures

HCL outpatient Version Number:6.0 Version Date:15/07/2019

- i) Change in auxological parameters (height, weight, BMI)
- ii) Change in total daily dose, including basal and bolus proportion, carbohydrate ratios and insulin sensitivity

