## 2. *Clinical*:

The difference between HCL insulin delivery vs standard therapy for the following measures

- i) Auxological parameters (height, weight, BMI)
- ii) Insulin delivery: total daily dose , including basal and bolus proportion, carbohydrate ratios and insulin sensitivity

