# 7 Design of the randomized controlled trial

# 7.1 Statement of design and randomisation

This is a prospective, randomized multi-centre study in adult and paediatric subjects from Australia, with type 1 diabetes mellitus aged 12 – 25 years. Participants can be on CSII or MDI treatment regimens to be eligible. After a run-in phase, subjects will be randomly assigned to one of the following two arms:

HCL arm: MiniMedTM 670G for 6 months; OR Conventional arm: MDI or CSII for 6 months.

Randomization will be stratified based on 4 variables: Time spent in target sensor glucose range (3.9 – 10mmol/L) – with participants evenly split above and below 55%(17) time in target range, age, diabetes duration, and centre site. This will be managed by the Clinical Trials Centre in Sydney.

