#### VISIT 6 (3 hours)

This visit is the randomization visit, and allocation is dependent on the stratifications listed previously.

The following data will be collected prior to randomization:

- Auxological i.
- a) Height, weight, BMI.
- ii. Diabetes clinical
- a) Blood pressure
- b) Previous 7 days' total daily dose insulin (including basal and bolus proportions)
- c) Carbohydrate ratios and insulin sensitivity factor
- d) Logbook will be collected. Symptomatic hypoglycaemia requiring carbohydrate rescue in the previous 14 days and time off work or school will be collected from the participant logbook
- iii) Biomarkers

A detailed description of sample preparation for biomarkers is found in appendix 15.9. 12mL of blood and 50mL of urine will be collected.

- a) Cell Adhesion Molecules (CAM)S
- b) Soluble vascular cell adhesion molecules sVCAM
- c) Soluble intercellular adhesion molecules sICAM
- d) s-e Selectin
- e) Oxidized Low density lipoprotein
- f) Myeloperoxidase.
- g) MicroRNA signatures for arterial, renal and retinal complications
- h) Telomerase
- i) DNA methylation/acetylation
- j) Glycomark
- k) Isoprostanes and proteomics
- 1) Clotting profile

Participant randomization will occur at the completion of the tasks above (for details on randomization process see section 7.3.1). Once randomized a date will be booked for entry into the study arm (visit 7), which should be no longer than 2 weeks after visit 6.

VISIT 7 (visit schedule dependent on randomization and baseline therapy)

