# THOSE RANDOMIZED TO STANDARD THERAPY

The study participant will attend the research facility to have a 4th generation sensor inserted and GST3C transmitter attached. Subjects will receive the following instruction:

- A) Expectations of minimum 4x/day glucose testing using CONTOUR® NEXT LINK 2.4 glucometer.
- b) Instructed to collect prospective data over the following 3 weeks and record into the logbook:
  - 1. Symptomatic hypoglycemia requiring carbohydrate rescue
  - 2. Time off work / school
  - 3. Insulin dosing (MDI participants)

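### Visits 11 and 16 collect basal and bolus proportions only from pump users, so that part of the insulin-delivery endpoint has no follow-up value for MDI controls

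*Protocol*

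**What the plan says.** Section 6.3 (2. Clinical) lists as a secondary endpoint the difference between HCL and standard therapy in "Insulin delivery: total daily dose , including basal and bolus proportion, carbohydrate ratios and insulin sensitivity". The matching objective in section 6.2.2 is put as a change: "Change in total daily dose, including basal and bolus proportion, carbohydrate ratios and insulin sensitivity". Section 6.2.2 defines standard therapy as MDI and CSII, and section 7.1 describes the control group as "Conventional arm: MDI or CSII for 6 months".

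The collection rules differ by visit:

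- At baseline (Visit 6) the item is "Previous 7 days' total daily dose insulin (including basal and bolus proportions", with no limit by regimen.
- At week 13 (Visit 11) and week 26 (Visit 16) the item becomes "Previous 7 days' total daily dose insulin (basal and bolus proportions for participants on insulin pump therapy", in the same words at both visits.
- The synopsis has no such limit. Its end-of-study list reads "Total daily dose, basal and bolus proportion, carbohydrate ratio and insulin sensitivity factor", and its midpoint list for Visit 11 is equally unrestricted.

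Separately, at Visits 9 and 12 participants in the standard-therapy arm are told to enter "Insulin dosing (MDI participants" in the logbook, for the two weeks before Visit 11 and the three weeks before week 26.

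**The concern.** The pump restriction appears only after randomisation, and it falls unevenly on the two arms. Participants who enter on MDI and are randomised to HCL are moved to a 670G pump at Visit 7, so at weeks 13 and 26 they are on insulin pump therapy and supply a split. Participants who enter on MDI and are randomised to standard therapy stay on injections and, under the visit wording, supply none. Whether a follow-up value exists then depends on arm and baseline regimen together.

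At stake is one component of one secondary endpoint. It is defined against MDI and CSII together, but the data as literally specified would support only HCL participants on a pump against CSII controls. Because this is a collection instruction, an analysis plan cannot restore a value that was never obtained. A repeated-measures model would in effect predict the missing MDI follow-up from CSII controls, since section 7.3 names baseline score, group, period and site as model terms, but not regimen. Baseline regimen is not among the four randomisation factors in section 7.1 either.

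**Working it through.** The plan states no figure on this point, so the check is mainly a reading of the passages side by side.

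**1. Who has a follow-up split if Visits 11 and 16 are followed literally**

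- Entered on CSII, randomised to HCL: on a pump, value recorded.
- Entered on MDI, randomised to HCL: moved to a pump at Visit 7, value recorded while on the pump.
- Entered on CSII, randomised to standard therapy: on a pump, value recorded.
- Entered on MDI, randomised to standard therapy: on injections, no value.

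Three of the four groups contribute. The missing one is the randomised counterpart of a group that is kept. Under the Visit 6 wording or the synopsis lists, all four contribute.

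**2. Which parts of the endpoint are affected**

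The restriction sits in a bracket attached to the split. At both visits total daily dose itself is asked of everyone, and carbohydrate ratios and insulin sensitivity are a separate item with no restriction. Only the basal and bolus proportion is affected.

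**3. What a bias would depend on**

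Let m be the MDI share at baseline, taken as equal in both arms. Let c_M and c_C be the mean changes in the split among MDI and CSII controls, and h_M and h_C the corresponding changes in the HCL arm.

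- Intended contrast: m(h_M − c_M) + (1 − m)(h_C − c_C).
- Contrast obtained: m·h_M + (1 − m)·h_C − c_C.
- Obtained minus intended: m(c_M − c_C).

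For an analysis of change, bias therefore needs MDI and CSII controls to change differently. A constant difference d in level between the two regimens cancels. For an analysis adjusted for baseline with slope b (taken as given), a constant d leaves m·d·(1 − b). This is zero at b = 1 and equals m·d only at b = 0, that is, without adjustment. The protocol gives none of m, d, b, c_M or c_C, so no figure for the bias follows from it.

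**4. Loss of precision, as an illustration**

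Inputs: 64 evaluable per arm (section 7.2) and an assumed CSII share p of controls between 0.3 and 0.8. All 64 HCL participants are assumed to contribute.

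The standard error is proportional to √(1/64 + 1/(64p)). Its ratio to the value with all controls is √((1 + 1/p)/2).

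- p = 0.3: 64 × 0.3 = 19.2 controls; ratio √(4.333/2) = 1.47; detectable difference at 80% power 0.73 SD.
- p = 0.5: 32 controls; ratio √(3/2) = 1.22; 0.61 SD.
- p = 0.8: 51.2 controls; ratio √(2.25/2) = 1.06; 0.53 SD.
- All 64 controls: 0.50 SD.

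**5. Whether the data could be obtained**

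MDI participants are told at Visit 3 to log insulin dosing, and Visit 6 then asks for the split from everyone. MDI controls get the same logging instruction at Visits 9 and 12, before Visits 11 and 16, and the logging windows are meant to cover the seven days before each. The eligibility criterion defines MDI by separate rapid-acting and long-acting injections, so the split can be computed if doses are logged by insulin type. The protocol does not say that they are.

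**The case against.** The strongest reply is that nothing need be lost. The synopsis is unrestricted, MDI controls log their doses in the right weeks, and logbooks are collected. On that view the bracket is loose wording.

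Part of this stands. The document does not settle that MDI proportions go uncollected, and a reader who concluded that the comparison is impossible would go beyond the text. But nothing links the dosing log to this endpoint. The same visit lists do name the logbook as the source for symptomatic hypoglycaemia, whereas the insulin item names no logbook and limits the split to pump users. Recovery is plausible but not assured.

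Three stronger readings are tempting and not supported:

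- **That the whole insulin-delivery endpoint ceases to be randomised.** Total daily dose, carbohydrate ratios and insulin sensitivity are collected from everyone.
- **That the entire HCL arm is set against CSII controls.** Section 15.11 keeps participants who stop HCL in follow-up, and some of them may no longer be on a pump.
- **That the bias can be sized.** A reader might take an assumed MDI share of 0.5 and an assumed level difference of 5 to 10 points and obtain 2.5 to 5 points. That describes unadjusted follow-up means. The objective is a change, and section 7.3 adjusts for baseline score, so a constant level difference largely cancels.

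Nor is it a bias in itself that the HCL change includes moving from injections to a pump. For MDI entrants that move is part of the randomised intervention. The difficulty is the absence of their control counterparts.

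**Conclusion.** The point holds as an internal contradiction with a definite consequence if the visit text is followed. The collection rule at Visits 11 and 16 conflicts with the endpoint, with Visit 6 and with the synopsis. It leaves the basal and bolus component without follow-up in MDI controls while pump-using former MDI participants in the HCL arm contribute. That component would then not compare the randomised arms.

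The direction and size of any bias cannot be derived from the protocol. The precision figures rest entirely on an assumed CSII share and on full data in the HCL arm. The primary endpoint is untouched. This is a minor point, worth correcting because the correction is simple and has to be made at data collection.

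**What to change.** At Visits 11 and 16 delete the restriction to participants on insulin pump therapy, so that both visits match Visit 6 and the synopsis. State that for MDI participants the split over the previous 7 days is computed from the insulin-dosing logbook already required from Visits 9 and 12, with long-acting (basal) and rapid-acting (bolus) doses recorded separately. Analyse the component by randomised arm.

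Two details should be settled in the same edit. The log should run up to the visit when a supplementary CGM week delays it. The same recording should also apply to any HCL-arm participant who is on injections at follow-up, because the HCL logbook instructions at Visits 9 and 12 contain no insulin-dosing item.

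If the sponsor does intend to collect the split from pump users only, the endpoint should say so and be limited to a comparison within participants who entered on CSII.

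The cost is a wording change at two visits and entry of seven days of logbook doses per MDI control at each. The downside is small: MDI doses are self-reported while pump doses are downloaded, and the report should say so.

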# Sensitivity analysis

The primary endpoint analysis will be re-run with the PP population as a sensitivity analysis. Secondary endpoints.

Coefficient of variation will be reported for each group: bootstrap methods will be used to estimate variability as appropriate.

Rates of hospitalisations for severe hypoglycaemia and moderate hypoglycaemia as per participant log will be analysed as unadjusted incidence rates based on the Poisson distribution. Incidence rates and incidence rate differences will be presented with their associated 95% confidence intervals calculated as exact Poisson confidence limits(22). In addition, where

HCL outpatient Version Number:6.0 Version Date:15/07/2019 appropriate Poisson or negative binomial regression models will be fitted e.g. moderate hypoglycaemia events from the participant log. If there are a high proportion of zero counts, zero inflated Poisson (ZIP) or zero inflated negative binomial models (ZINB) will be considered. If counts are sparse then rates will be reported descriptively only. Number of hospitalisations due to diabetic ketoacidosis events and other safety outcomes will be tabulated and presented as n and %.

Continuous outcome measures (including psychosocial) collected at baseline and endpoint will be analysed using ANCOVA adjusting for baseline score and site. Measures collected at baseline, 3 months and endpoint (e.g. *HbA1c*, *Fasting capillary blood glucose*, *Mean CGM glucose*, *Hypoglycaemic Fear Survey-II Worry scale*, *Child State-Trait Anxiety Inventory*, *The Diabetes Treatment Satisfaction Questionnaire status and change version*, *Problem Areas in Diabetes, Impaired awareness of hypoglycaemia: GOLD SCORE, INSPIRE questionnaires*) will be analysed using mixed models repeated measures (MMRM) adjusting for baseline score (where appropriate), group, period (baseline, 3 months, 6 months) and site. A random intercept term for 'individual' will also be employed if deemed appropriate. Least square means and least square mean differences and their associated 95% confidence intervals will be presented for each group and between groups. Unstructured covariance matrix will be used unless other covariance structures are more appropriate as determined by the Bayesian information criteria (BIC). Human technology interaction and health care professional experiences and expectations analyses will be reported Exploratory; descriptive analysis.

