# VISIT 3 (1.5 hrs)

This visit starts the official glycaemic baseline data collection point. This constitutes 21 days of blinded continuous glucose monitoring. The study participant will attend the research facility to have a 4th generation sensor inserted and GST3C minilink attached. Subjects will receive the following instruction:

- i. Expectations of minimum 4x/day glucose testing using CONTOUR® NEXT LINK 2.4 glucometer. Participants will be instructed that an addition to any glucose values recorded on their usual glucometer, they will need 4x additional values (can be taken concurrently) taken on a CONTOUR® NEXT LINK 2.4 glucometer which will be issued to them at this visit.
- ii. Instructed to collect prospective data over the following 21-28 days and record into the diary:
  - 1. Symptomatic hypoglycaemia requiring carbohydrate rescue
  - 2. Time off work / school (including parents)
  - 3. Insulin dosing (MDI participants)
- iii. Instruction on the logbook, with respect to identifying contacts (investigative staff) for trouble shooting and technical issues for the following 21-28 days.

At this visit, all participants will be issued with the following:

- i. Participant logbook
- ii. CONTOUR® NEXT LINK 2.4 glucometer

VISIT 4 and Visit 5 (30 minutes each)

7 days after sensor insertion, participants will return to download the first week of CGM data. The CONTOUR® NEXT LINK 2.4 glucometer will be uploaded. A new sensor will be inserted and a fresh GST3C attached. The logbook will be revised, and participants reminded to keep records accurate and up to date. This is repeated in another 7 days. If there is insufficient CGM data collected by visit 5 (>70% of of each 7 day period having CGM recordings),or due to a technical reason for the CGM data not being available for the minimum amount, participants will be offered additional CGM collection to meet the requirement of the protocol.

HCL outpatient Version Number:6.0 Version Date:15/07/2019

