## ii. THOSE RANDOMIZED TO HCL

Participants will have a 2nd, 4th generation sensor inserted andGST3C transmitter attached. Subjects will receive the following instruction:

- a) Expectations of minimum 4x/day glucose testing using CONTOUR® NEXT LINK 2.4 glucometer.
- b) Instructed to collect prospective data over the following 2 weeks and record into the logbook:
  - 1. Symptomatic hypoglycaemia requiring carbohydrate rescue
  - 2. Time off work / school

VISIT 10 (12 weeks from Visit 7), 30 minutes).

7 days after sensor insertion, participants will return to download the first week of CGM data. The CONTOUR® NEXT LINK 2.4 glucometer will be uploaded. A new sensor will be inserted and a fresh GST3C attached. The logbook will be revised, and participants reminded to keep records accurate and up to date.

VISIT 11: (13weeks since Visit 7), 4 hours).

All participants will have a clinical review of insulin settings (MDI, CSII and HCL) and refresher on carbohydrate counting. An additional CGM week and visit will be required if there is <70% of available CGM time available from the upload.

The following data will be collected at the midpoint:

- i. Auxological
  - a. Height, weight, BMI
- ii. Glycaemic:
  - a. CGM uploaded for standard therapy on MDI and CSII
  - b. 670G uploaded for HCL participants
- iii. Diabetes clinical
  - a. HbA1c
  - b. Blood pressure (average of 2 readings)
  - c. Previous 7 days' total daily dose insulin (basal and bolus proportions for participants on insulin pump therapy)
  - d. Carbohydrate ratios and insulin sensitivity
  - e. Symptomatic hypoglycaemia requiring carbohydrate rescue in the previous 14 days from participant logbook.
- Psychological assessments: iv.
  - a. Fear of hypoglycaemia: Hypoglycaemic Fear Survey-II Worry scale: 17-<25years. Children's Hypoglycaemia Fear survey 12 – 17 years.
  - b. Hypoglycaemia Awareness: Hypoglycaemia Awareness Scale (Gold Score) (all ages)
  - c. Anxiety: State-Trait Anxiety Inventory (Child version for 12-15yrs, adult version >16-<25vrs).
  - d. Impact and Satisfaction: The Diabetes Treatment Satisfaction Questionnaire status and change version (16 - <25 years)
  - e. Quality of Life: 12-<25 years: EQ-5D-Y,
  - f. **Diabetes specific quality of life**: PedsQL Child version (12 years), Adolescent version (13 – 18 years) and young adult version (18 – <25 years).

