  - g. **Diabetes distress:** *Problem Areas in Diabetes (Teen version for 12 17 years,*  $standard\ version \ge 17 - <25 yrs)$

Participants will be issued a third logbook for the second half of the study documenting symptomatic hypoglycaemia requiring carbohydrate rescue and interruptions from work/school, and document any insulin pump technical issues (insulin infusion site failures, sensor changes, unplanned exit from HCL).

Participants will be issued with enough consumables for the remainder of the study.

VISIT 12: week 23 from Visit 7. (30 minutes)

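### Logged hypoglycaemia is committed to an unadjusted between-arm rate comparison although a pre-randomisation count is collected, and the log extraction windows do not line up

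*Protocol*

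**What the plan says.** **Baseline.** At Visit 3 participants are "Instructed to collect prospective data over the following 21-28 days and record into the diary", and symptomatic lows treated with carbohydrate are the first item. At Visit 6, before randomisation, the entry reads "Symptomatic hypoglycaemia requiring carbohydrate rescue in the previous 14 days and time off work or school will be collected from the participant logbook".

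**Second half.** At Visit 11, week 13, "Participants will be issued a third logbook for the second half of the study documenting symptomatic hypoglycaemia requiring carbohydrate rescue". Visit 12 (week 23) then gives a fresh logging instruction that differs by arm: three weeks for standard therapy, two weeks for HCL. Visit 16 collects "Symptomatic hypoglycaemia requiring carbohydrate rescue in the previous 21 days from participant logbook" in both arms, and the logbooks are handed back.

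**Analysis.** Under secondary endpoints in section 7.3, "moderate hypoglycaemia as per participant log will be analysed as unadjusted incidence rates based on the Poisson distribution", with rates and rate differences and their 95% limits. The section then allows Poisson or negative binomial regression where suitable, gives this outcome as its example, and names no covariates or offset. In the same section, continuous outcomes are adjusted for baseline score and site.

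**The concern.** The only unconditional analysis of logged hypoglycaemia ignores the best available predictor of a person's later rate, namely the same person's rate before randomisation. That count is already collected. If people differ consistently in how often they log lows, an unadjusted comparison carries between-person variation that adjustment would remove.

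Three details of the log need tidying before such a model can be run properly:

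- The baseline extraction (14 days) is shorter than both the diary that was kept and the end extraction (21 days).
- The Visit 12 logging periods differ by arm, but the Visit 16 extraction does not.
- Section 7.3 speaks of moderate hypoglycaemia, whereas the visit schedule logs symptomatic lows treated with carbohydrate. The protocol never says that these are the same event.

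**Working it through.** The protocol gives no precision or power figure for logged hypoglycaemia, so there is none to reproduce.

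**1. Day counts**

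- Baseline: 14 days taken from 21 to 28 kept, so 14/21 = 67% down to 14/28 = 50%.
- Second half: weeks 13 to 26 are 13 × 7 = 91 days, approximately, given the visit windows. The extraction is 21/91 = 23%.
- Visit 12: 21 days of logging instructed in standard therapy, 14 in HCL, and 21 extracted in both.

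**2. Effect of baseline adjustment**

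Inputs from the protocol are n = 64 evaluable per arm (section 7.2: 80 less 20% drop-out), a follow-up window of 3 weeks and a baseline window of 2 weeks. Assumed, because the protocol gives none of them:

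- event rate λ from 0.25 to 4 per person-week;
- negative binomial dispersion k from 0 to 1.5;
- correlation ρ of the underlying personal rates between baseline and follow-up, from 0.5 to 0.8.

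Formulas, with T in weeks and equal rates in the arms:

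- v(T) = 1/(λT) + k
- SE of the log rate ratio, unadjusted = √[(2/n) · v(T)]
- observed correlation r = ρk / √[v(T_base) · v(T_follow)]
- SE ratio, adjusted to unadjusted = √(1 − r²); n cancels

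Worked case with λ = 1, k = 0.5, ρ = 0.8:

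- v(2) = 0.5 + 0.5 = 1.0 and v(3) = 0.333 + 0.5 = 0.833.
- Unadjusted SE = √(0.03125 × 0.833) = 0.161.
- 14-day baseline: r = 0.4/√(1.0 × 0.833) = 0.438, so the ratio is √(1 − 0.192) = 0.899 and the SE is 0.145.
- 21-day baseline: r = 0.4/0.833 = 0.48, so the ratio is √(1 − 0.230) = 0.877.

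| λ per week | k | ρ | SE ratio, 14-day baseline | SE ratio, 21-day baseline |
|---|---|---|---|---|
| 0.25 | 0.25 | 0.5 | 0.998 | 0.997 |
| 1 | 0.5 | 0.5 | 0.962 | 0.954 |
| 1 | 0.5 | 0.8 | 0.899 | 0.877 |
| 2 | 1.0 | 0.8 | 0.749 | 0.728 |
| 4 | 1.5 | 0.8 | 0.664 | 0.652 |

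The first and last rows are the extremes for k > 0. With k = 0 there is no between-person variation and adjustment gains nothing. Most of the gain comes from adjusting at all. Lengthening the baseline from 14 to 21 days adds at most a few hundredths in these cases.

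**3. Longer end window, for comparison**

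Using 91 instead of 21 days without adjustment gives √[v(13)/v(3)]. That is 0.48 if k = 0, and 0.59 to 0.98 over the overdispersed range. At λ = 1, k = 0.5 it is √(0.577/0.833) = 0.83.

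**4. Unequal logging**

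If HCL participants logged for 14 days only and 21 were used as denominator, their apparent rate would be 14/21 = 0.67 of the true rate. This is the extreme case, because the third logbook separately asks for entries throughout the second half.

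**The case against.** Section 7.3 already names the negative binomial family for this very outcome, and covariates and offset are details that an analysis plan may supply. That is right as far as it goes: baseline adjustment is not ruled out, and its absence from the protocol is not in itself an error. What stands is that the one analysis stated without condition is unadjusted.

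The outcome is also a minor one. Logged lows are not among the listed glycaemic endpoints. The hypoglycaemia hypothesis concerns sensor time below 3.9 mmol/L, and section 7.2 powers it on sensor data. Hypoglycaemic events do enter the economic analysis, but undefined. This limits the weight of the point.

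Four stronger readings are tempting, and the documents do not support them:

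- *The remaining log days are thrown away.* A reader might infer this from the Visit 16 line. But whole logbooks are handed in, and section 7.3 does not fix the window that it analyses. Those days are not listed for extraction, which is less than being discarded.
- *Going from 14 to 21 days inflates events by half.* This is true of raw counts only. Section 7.3 uses rates, which divide by time, and the extraction windows are the same in both arms.
- *The 91-day log should be the main window.* The 21 days coincide with the week 23 to 26 sensor block of the primary endpoint and follow a fresh instruction and weekly reminders. No visit is scheduled between weeks 13 and 23, and under-recording there could differ by arm. Precision is traded against supervised recording.
- *A large gain is assured.* The full second-half log plus a 21-day baseline gives ratios of 0.58 to 0.86 on the assumed grid, but this needs both changes and inputs that the protocol does not state.

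**Conclusion.** The point holds as a modest gain in precision and a clean-up of the log data, for an outcome outside the listed glycaemic endpoints. The pre-randomisation count is collected but has no committed role, and the definite comparison is unadjusted. Adjusting the 21-day comparison for the 14-day baseline gives an SE ratio between about 0.66 and just under 1.00. The lower end needs frequent events, strong between-person variation and ρ = 0.8. With rare events or little variation the gain is negligible. The size rests wholly on assumed rate, dispersion and correlation, and only the direction can be stated with confidence.

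The arm difference in the Visit 12 logging instruction is a contradiction within the protocol. Unlike the 14-day against 21-day mismatch, it could bias the comparison if a fixed denominator were used.

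**What to change.** 1. At Visit 6, extract at least the full 21-day baseline sensor block from the diary.
2. In section 7.3, make the between-arm comparison of logged events a negative binomial model. Use the log of days actually logged as offset, and the log baseline rate (with a small constant added for zero counts) and site as covariates. Keep the unadjusted rates as descriptive results.
3. Keep the 21 days at Visit 16 as the main window, aligned with the week 23 to 26 sensor block. Enter the rest of the third logbook, about 91 days in all, for a supportive analysis.
4. Reconcile the Visit 12 logging periods in the two arms with each other, with the 21-day extraction and with the second-half logbook.
5. State whether moderate hypoglycaemia from the participant log means the logged symptomatic lows treated with carbohydrate.

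The cost is additional logbook data entry and edits to the Visit 6, Visit 12 and section 7.3 text. Nothing new is asked of participants unless the reconciled logging period is longer than the one that an arm is now given.
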